5.6 Total Expected Duration of the Clinical Investigation

Subjects will be followed for 15-months after their initial ablation procedure

5.7 Expected Duration of Each Subject's Participation

Scheduled visits and data collection for the trial will occur at baseline, procedure, and pre-discharge as well as at scheduled follow-up visits at 7-days (phone call), 3-months (in-person), 6-months (phone call), 12-months (phone call) and 15-months (in-person) post-procedure. Subjects will be exited from the trial at the conclusion of their 15-month follow-up visit.

5.8 Number of Subjects

Two hundred twenty-four (224) subjects will be enrolled in this clinical investigation at up to 25 sites worldwide for analysis of the primary endpoints. No center may contribute more than 20% of the total number of enrollments without Sponsor pre-approval and at least 50% of the subjects must be from the United States.

6 TREATMENT AND EVALUATION OF ENDPOINTS

The Principal Investigator is responsible for ensuring all clinical investigation data is collected as outlined in this CIP. However, other site personnel may obtain data to be used in the trial. Physical exams and adverse event assessment may be performed by an investigator, physician, or mid-level provider (i.e. nurse practitioners, physician assistants, or fellows). The neurological assessment needs to be performed by a qualified physician and the NIH Stroke Scale must be administered by a certified assessor.

6.1 Baseline Clinical Assessments

The assessments listed below will be collected from each subject at the Baseline Visit. Information gathered at this visit will be used to verify eligibility of the subject for the trial.

- Documentation of the informed consent process as defined in **Section 5.2.2**
- Demographics
- Medical history, cardiac arrhythmia history, and documentation for the diagnosis of persistent AF
- Healthcare utilization documentation for cardiovascular-related hospitalizations, emergency room and/or urgent care visits during the 12-month period prior to consent

- Administration of a 24-hour Holter that must demonstrate 100% continuous AF within 90-days of the procedure OR documentation of 2 ECGs (from any form of rhythm monitoring) taken at least 7 days apart showing continuous AF

NOTE: Repeat Holter assessments are not allowed if 100% continuous AF was not demonstrated on the first 24-hour Holter assessment. If artifact is present in the tracing, it can be disregarded when assessing for 100% continuous AF. All readable portions of the tracing should demonstrate continuous AF (non-sinus rhythm).

- AAD history, including maximum ineffective dosages and dosages not tolerated
- Anticoagulation drug usage
- Complete physical exam including 12-lead ECG, NYHA assessment, and CHA₂DS₂VASc score assessment

NOTE: If these assessments were performed as part of standard of care prior to consent, they may be used if they were completed within 30-days of the initial ablation procedure.

- Neurological assessment by a qualified physician and administration of the NIH Stroke Scale (NIHSS) by a certified assessor must be performed within 14-days of the ablation procedure.

NOTE: Subjects with new findings on the neurologic assessment/NIHSS are required to have a formal neurological consult and follow-up diffusion-weighted magnetic resonance imaging (MRI) of the brain. If contra-indicated for MRI, then an alternate form of imaging may be performed.

- Echocardiography or CT results (LVEF and LAD assessments) obtained within 6-months of the ablation procedure may be used to meet eligibility criteria and documented at baseline, with the exception of thrombus assessment. Thrombus assessment must be performed as specified in **Section 6.2.6**.
- Administration of the AF Effect on Quality of Life Survey (AFEQT) and EuroQoL Five Dimensions Questionnaire (EQ-5D-5L) quality of life questionnaires
- Documentation of adverse events and protocol deviations that occur after consent and prior to the procedure

6.2 Peri-procedural Considerations

6.2.1 Anticoagulation

The anticoagulation strategies from the 2017 Expert Consensus Statement on Catheter and Surgical Ablation for AF⁴ for pre- and post-ablation are outlined below and are recommended to be followed for management of study subjects. However, **it is strongly recommended that a strategy of uninterrupted anti-coagulation be in place for peri-operative management**. All start and stop times of anticoagulants must be documented for the trial. Subjects who are taking coumadin or warfarin will have international normalized ratio (INR) values documented on the day of the procedure and after the drug is restarted after the ablation procedure.

Pre-ablation

- Patients who are therapeutically anticoagulated with warfarin, dabigatran or rivaroxaban prior to the ablation are recommended to have the ablation procedure performed without interruption of the anticoagulant.

- Patients anticoagulated with a novel oral anticoagulant (NOAC) prior to undergoing an AF ablation procedure may have one to two doses of the NOAC withheld prior to AF ablation with re-initiation of the NOAC post-ablation.
- Anticoagulation guidelines that pertain to cardioversion of AF should be adhered to in patients who present for an AF ablation procedure.

Post-ablation

- In patients who are not therapeutically anticoagulated prior to catheter ablation of AF and in whom warfarin will be used for anticoagulation post-ablation, low molecular weight heparin or intravenous heparin should be used as a bridge for initiation of systemic anticoagulation with warfarin following AF ablation.
- Systemic anticoagulation with warfarin or NOAC is recommended for at least 2-months post-ablation of AF. Systemic anticoagulation beyond 2-months post-ablation should be based on the patient's stroke risk profile (not on the perceived success or failure of the ablation procedure).
- In patients who have not been anticoagulated prior to catheter ablation of AF or in whom anticoagulation with a NOAC or warfarin has been interrupted prior to ablation, administration of a NOAC 3 to 5 hours after achievement of hemostasis is reasonable post-ablation.

6.2.2 Antiarrhythmic Drug Therapy

The 2017 Consensus Statement on Catheter and Surgical Ablation for Atrial Fibrillation⁴ states that AADs need to be discontinued for at least five half-lives and beta-blockers withheld for at least 24-hours prior to the ablation procedure if a strategy searching for non-pulmonary vein triggers is employed. As the ablation strategy is left to the discretion of the investigator, other than the requirement for PV isolation, this clinical investigation will not require that all subjects discontinue AADs for at least five half-lives. However, AAD usage (start and stop date, time, frequency and dose information) will be documented for the trial prior to and after the subject's procedure(s).

During the blanking period after the ablation procedure, it is recommended that any current AAD medication be continued following the ablation procedure to aid with healing. Current AADs should be withdrawn 4-6 weeks after ablation, unless clinically contraindicated, to assess for recurrence of symptoms and for determination of the need for a repeat ablation during the blanking or therapy consolidation periods. It is recommended that sites phone subjects 4-6 weeks after ablation to remind them to discontinue their AAD medication.

It is recommended that subjects be taken off all Class I and III AADs prescribed for AF/AFL/AT after the blanking and therapy consolidation periods. If the investigator feels that the subject may benefit from a Class I or III AAD during the 9-month evaluation period (post-blanking and therapy consolidation periods), then the investigator should first prescribe a previously ineffective Class I or III AAD up to the historic maximum ineffective dose prior to the ablation procedure. If the historic maximum ineffective dose remains ineffective then a new Class I or III AAD may be initiated.

Subjects using AADs without documented AF/AFL/AT recurrence during the follow-up period will not be considered effectiveness endpoint failures. However, if the subject requires a new AAD or a previously

failed AAD at a dose greater than the highest ineffective historical dose for AF after the therapy consolidation period (>180 days post-procedure), they will be considered a primary effectiveness endpoint failure.

6.2.3 Vascular Access

It is strongly recommended that vascular access be obtained using ultrasound to minimize complications.

6.2.4 Esophageal Temperature Monitoring

It is strongly recommended that esophageal temperature be monitored using an esophageal temperature probe at the anatomical location nearest the site of energy delivery. Alternatively, esophageal deviation may be performed when ablating near the esophagus.

Termination of energy is strongly recommended if a >1°C rise in esophageal temperature is observed.

6.2.5 Pregnancy Testing

A urine pregnancy test should be performed for women of child-bearing potential, preferably on the day of the procedure.

6.2.6 Thrombus Assessment

Left atrial thrombus assessment by transesophageal echocardiography (TEE) (recommended method) must be performed within one day of the ablation procedure (the day before or the day of the ablation procedure). Alternatively, phased-array intracardiac echocardiography (ICE) or TEE assessment can be performed on the day of the procedure, if the presence of thrombus has not been ruled out prior to the procedure. Standard of care may be used for this assessment.

If a thrombus is discovered within a day of the procedure, the procedure should be postponed and the subject placed on anticoagulation until the thrombus is resolved and confirmed by imaging. Once confirmation is obtained demonstrating resolution of the thrombus, the inclusion/exclusion criteria should be re-reviewed for the subject to confirm continued eligibility for the trial. The neurological assessment and NIH Stroke Scale must be repeated within 2-weeks of the newly scheduled procedure and these assessments used to determine if the subject still meets eligibility for inclusion in the trial.

The subject will not need to be re-consented for the trial after the thrombus resolves, provided that the subject meets all eligibility criteria and will undergo an ablation procedure within 90-days of the original consent date unless otherwise indicated by the governing IRB/EC.

6.3 Ablation Procedure

Any subject who does not meet eligibility requirements will be a screen failure and will be excluded from this trial and will not have the TactiCath SE catheter inserted into their vasculature.

For those subjects meeting eligibility criteria and are enrolled in the trial, it is preferable that the ablation procedure be performed within 14-days of consent. Use of robotic systems or Stereotaxis to assist with the procedure is not allowed.

The subject's rhythm when they enter the EP lab will be documented for the trial. All cardioversions that occur from the time the subject enters the lab to the start of the procedure and during the procedure will be documented.

It is recommended that heparin be administered prior to trans-septal puncture during the AF catheter ablation procedure and adjusted to achieve and maintain an ACT of at least 300 seconds. Use of an ICE probe during the procedure to guide septal puncture and to monitor catheter position and manipulation is strongly recommended. Administration of protamine to reverse heparin is acceptable.

Following trans-septal access, a standard treatment scheme for mapping and ablation should be conducted. Physicians performing ablations must be qualified operators and trained on the study. Each physician who ablates during a particular case needs to be documented on the Procedure CRF. Fellows will not be allowed to perform ablations unless an exception is made by Abbott's Medical Director in writing prior to the fellow performing ablations for this trial.

The procedure should be performed according to the TactiCath SE *Instructions for Use* document using the recommended ablation parameters as noted in the document:

- Power (10 - 30W)
- Contact force (target 20 g, 10-30 g)
- Temperature (37 – 50 °C)
- Irrigation flow rate (17 - 30 ml/min)

When ablating near the left atrial posterior wall, it is recommended that a minimum targeted contact force of 5-10 grams be used as specified in the 2017 HRS Consensus Statement. Recommended maximum parameters for ablating the left atrial posterior wall near the esophagus are:

- Contact force: ≤ 15 g for ≤ 10 seconds
- Power: up to 40W

The following ablation strategy should be followed for all subjects:

1. Perform wide area circumferential ablation to electrically isolate the pulmonary veins.
2. Administer isoproterenol following initial pulmonary vein isolation if the subject is in sinus rhythm to identify gaps in ablation and to identify and ablate any additional AF triggers.
3. Cardiovert the subject before isoproterenol challenge if he/she is not in sinus rhythm after initial pulmonary vein isolation.
4. Ablation of additional cardiac substrate (e.g. ablation of complex fractionated atrial electrograms (CFAE) or linear ablations) should only be considered if sinus rhythm is not restored after isolation of the pulmonary veins and ablation of non-PV triggers.

All subjects will receive ablations to achieve electrical isolation of the PVs. A minimum 20-minute wait period following electrical isolation of all PVs is required. Achievement of electrical isolation of the PVs requires assessment and documentation of entrance block. It is recommended that exit block also be demonstrated.

If PV reconnection occurs during or after the 20-minute wait period following initial PV isolation of all veins, the vein(s) that reconnected and whether it was successfully isolated after administration of additional ablation lesions will be documented on the CRF. Another 20-minute waiting period is not required after performing touch-up ablation lesions for reconnected PVs.

Subjects with a history of AFL, AT or other SVT (spontaneous or induced) or if these arrhythmias are induced at the time of AF ablation, may undergo additional targeted ablation as clinically indicated. All subjects with a history of typical atrial flutter or induced cavotricuspid isthmus (CTI)-dependent atrial flutter need to undergo concomitant AFL ablation and are required to verify bi-directional block by mapping and pacing maneuvers after initial bi-directional block is achieved.

Additional non-pulmonary vein AF ablation targets (e.g. linear ablation, elimination of CFAEs, rotational activity, autonomic ganglia, isolation of the left atrial appendage, ablation of scar identified by voltage mapping or MRI, and non-PV triggers) are permitted per the investigator's discretion and will be documented for the trial if sinus rhythm is not restored after isolation of the pulmonary veins and ablation of non-PV triggers. If a linear ablation strategy is used, documentation of bidirectional block across the ablation line must be demonstrated and assessed in sinus rhythm and with differential pacing maneuvers. High-dose isoproterenol may be administered to screen for and ablate non-PV triggers. If CFAEs, rotational activity, or non-PV triggers are ablated, the acute goal is elimination of CFAEs, rotational activity, and non-PV triggers and AF termination.

The goal is that the subject is in sinus rhythm at the end of the procedure. If AF cannot be terminated by ablation at the conclusion of the procedure, it is recommended that the patient be cardioverted and PV isolation rechecked.

Verify that the subject has not experienced pericardial effusion by ICE or transthoracic echocardiogram (TTE) at the end of the procedure.

The data from the entire procedure recorded on the commercial EnSite system should be anonymized and labeled with the study information, Subject ID, backed up on a USB or external drive, and sent to Abbott within a reasonable time frame (within 10 days).

If for any reason, the subject has the TactiCath SE inserted into their vasculature, but no ablation is performed and the subject will not be rescheduled to receive another ablation procedure, the subject will be followed for 30-days to assess safety and then exited from the trial. Follow-up at 30-days will be conducted via a phone call to the subject (may also be an on-site visit). Subjects who will have their ablation procedure re-scheduled will not need to be re-consented for the trial provided they are rescreened (all eligibility criteria met prior to the procedure) within 90-days of the initial consent date.

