4.1 Primary Endpoint

4.1.1 Primary Safety Endpoint

The primary safety endpoint is the rate of device and/or procedure-related serious adverse events with onset within 7-days of any ablation procedure that uses the TactiCath SE catheter (initial or repeat procedure performed ≤ 180 days of initial procedure) that are defined below:

- Atrioesophageal fistula¹
- Cardiac tamponade/perforation¹
- Death
- Heart block
- Myocardial infarction (MI)
- Pericarditis²
- Phrenic nerve injury resulting in diaphragmatic paralysis
- Pneumothorax
- Pulmonary edema (respiratory insufficiency)
- Pulmonary vein stenosis¹
- Stroke/cerebrovascular accident (CVA)
- Thromboembolism
- Transient ischemic attack
- Vascular access complications (including major bleeding events³)

-
1. Atrioesophageal fistula, cardiac tamponade/perforation and pulmonary vein stenosis will be evaluated through 15-months.
 2. Pericarditis is a common occurrence for almost all procedures and will only be considered a primary safety endpoint event if the pericarditis pleuritic symptoms last longer than 7-days and/or requires hospitalization of greater than 24 hours for reasons other than for observational purposes only.
 3. Bleeding is a major complication of AF ablation if it requires and/or is treated with transfusion or results in a 20% or greater fall in hematocrit.

Definitions regarding the primary safety events are provided in **Appendix III**.

Serious AF/atrial flutter (AFL)/atrial tachycardia (AT) recurrences without coexisting conditions (e.g. thromboembolism, worsening heart failure, etc.) will be counted as effectiveness failures but will not count against the primary safety endpoint.

The performance goal is set at [REDACTED] as determined by relevant studies for persistent AF that utilize radiofrequency ablation. Refer to the Statistical Analysis Plan for details regarding the rationale for the performance goal.

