6.6.1 Repeat Ablation Procedures

One ablation procedure is allowed during the blanking and therapy consolidation periods (within 180 days post-initial procedure) due to AF/AFL/AT recurrence without being considered an effectiveness endpoint failure. The repeat procedure must be performed with the TactiCath SE catheter using the recommended parameters listed in the *Instructions for Use* document and in **Section 6.3**. The TactiCath SE catheter should not be used for repeat procedures that occur ≥ 181 days after the initial procedure or if the subject requires a third ablation procedure at any time during the follow-up period.

Certain assessments need to be performed if a repeat ablation is required. Neurological assessment and administration of the NIHSS by a certified assessor must be performed within 14-days of the repeat ablation procedure. Thrombus assessment must be performed as outlined in **Section 6.2.6** prior to ablating the subject. Verification of the exclusion of pericardial effusion by ICE or TTE must also be performed prior to the conclusion of the procedure.

A 7-day (± 2 days) follow-up phone call to the subject will need to be conducted after the repeat procedure. All other follow-up visits will occur as previously scheduled from the initial ablation procedure. Note that the 90-day blanking period followed by a 90-day therapy consolidation period are still in place from the initial procedure.

If AF/AFL/AT recurrence (>30 second episode) occurs at any time after this second ablation procedure or after the therapy consolidation period (≥ 181 days post-initial procedure), the subject will be considered an effectiveness endpoint failure. If the subject requires a repeat procedure for AF/AFL/AT recurrence after the therapy consolidation period or the subject requires a third ablation procedure, then the subject will be considered an effectiveness endpoint failure regardless of documentation of a >30 second AF/AFL/AT episode.

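### Section 6.3 gives a general power range of 10 to 30 W and a 40 W maximum near the esophagus, and does not say which governs

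*Protocol*

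**What the plan says.** Protocol Section 6.3 directs that the procedure follow the catheter's Instructions for Use, "using the recommended ablation parameters as noted in the document". It restates four parameters. Power is 10 to 30 W, and the force entry reads "Contact force (target 20 g, 10-30 g". None of the four lines carries an anatomical qualifier.

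The next paragraph turns to the posterior wall of the left atrium. It first recommends a minimum targeted contact force of 5 to 10 g, citing the 2017 consensus statement. It then introduces a second list: "Recommended maximum parameters for ablating the left atrial posterior wall near the esophagus are". That list has two lines, "Contact force: ≤ 15 g for ≤ 10 seconds" and "Power: up to 40W". No source is given for either.

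Section 6.6.1 covers repeat ablation within 180 days: "The repeat procedure must be performed with the TactiCath SE catheter using the recommended parameters listed in the" Instructions for Use and in Section 6.3. Section 2.2.1 says that devices outside the United States are used in line with approved labeling, the Instructions for Use and standard-of-care guidelines.

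**The concern.** The two power statements come from the same section and overlap only in part. An operator working on the posterior wall near the esophagus at more than 30 W is within the regional maximum and outside the range that Section 6.3 attributes to the Instructions for Use. The text does not say which statement takes precedence.

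The site matters because of the primary safety endpoint. Section 4.1.1 states that "Atrioesophageal fistula, cardiac tamponade/perforation and pulmonary vein stenosis will be evaluated through 15-months", so fistula is counted well beyond the 7-day window that applies to most components. Operators should not have two unreconciled limits where the protocol itself singles out the esophagus.

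There is also a conduct question. Section 10.5 allows no waivers and requires every deviation to be reported. The readable text does not say whether a posterior-wall lesion above 30 W is a deviation, so sites and monitors could answer differently.

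**Working it through.** The plan gives no statistic to reproduce here. The check sets the two lists in Section 6.3 side by side and looks for any sentence that ranks them.

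| Parameter | General list (Instructions for Use as restated in Section 6.3) | Posterior-wall paragraph | Change |
|---|---|---|---|
| Power, upper limit | 30 W | 40 W | 40 − 30 = +10 W; 10/30 = +33% |
| Contact force, upper limit | 30 g | 15 g, for at most 10 seconds | 15 − 30 = −15 g; −15/30 = −50% |
| Contact force, lower end | 10 g | minimum target of 5 to 10 g | 5 − 10 = −5 g at its lowest |

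**Where the power statements agree.** The general list covers 10 to 30 W and the regional list covers anything up to 40 W. Powers of 10 to 30 W satisfy both. Powers above 30 W and up to 40 W satisfy only the regional list. That band is unreconciled.

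**Whether the layout explains it.** Both regional force figures move down from the general range. The power ceiling alone moves up. The 10-second limit is printed on the force line only, so a reader cannot tell whether it also conditions the power line. The consensus statement is cited for the minimum force and not for the list of maxima.

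**Whether other text settles it.**

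- Section 6.6.1 uses binding language for repeat procedures but points to both sources, so it carries the discrepancy forward.
- Section 2.2.1 points sites outside the United States to labeling, the Instructions for Use and standard-of-care guidelines, and does not mention the 40 W line. Under Section 5.8 at least half of the subjects come from the United States, and that sentence does not apply to them.
- Section 6.2.4 says "Termination of energy is strongly recommended if a" rise in esophageal temperature of more than 1 °C is observed. This is a separate safeguard and names no power.
- The readable parts of the SAP do not address power.

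No readable sentence in either document ranks the two statements.

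**The case against.** The best counter-argument is that a specific instruction overrides a general one. The second list is limited by anatomy and follows a general list, and such a list is normally read as the rule for its region. The 5 to 10 g minimum already reaches below the general force range and has a named source, which suggests deliberate regional guidance. The general force target of 20 g also lies above the regional ceiling of 15 g, so for force the regional line must displace the general target. Further, 40 W is a ceiling and not a target, both lists are recommendations, and an operator who stays at 10 to 30 W meets every statement. Ablating physicians must have contact force experience under Section 10.3.2.

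Much of this stands. The 40 W line may be intended, and no operator is forced to breach either statement. But the precedence has to be inferred. The list is labelled as maxima and not as an exception to the Instructions for Use, and the procedure as a whole is directed to follow that document. The sourced force minimum does not explain an unsourced power line that moves the other way.

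The limits of the evidence also stand. The Instructions for Use is not among the documents, so the absence of a regional exception is confirmed only for the parameters as Section 6.3 restates them. The revision history and the per-protocol definition are redacted. A recorded reason for the 40 W line, or a rule on how such lesions are classified, could exist there.

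**Conclusion.** The concern holds. Section 6.3 contains two recommended power statements that differ by 10 W (33%) at their upper ends, with a band above 30 W and up to 40 W that fits only one of them. Reading the regional line as an exception is possible but is not stated.

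This is a problem of internal consistency in safety-relevant guidance. The percentages describe the gap between the two figures and do not measure a consequence. The effect on the rate of fistula or any other event cannot be computed from the documents, and no effect on any analysis is claimed. The conclusion rests on the readable text of the protocol and SAP. It should be corrected, and it takes no position on which power figure is right.

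**What to change.** The sponsor should reconcile the two power statements in Section 6.3 with each other and with the Instructions for Use. The revised text should:

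- state which statement governs at the posterior wall near the esophagus;
- say whether the 10-second condition applies to the power line as well as the force line;
- make sure the cross-reference in Section 6.6.1 then points to a single consistent set of parameters.

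If the 40 W line is a deliberate exception, one sentence saying so would resolve the point. Sites should be told of the clarification.

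The cost is a wording change and a site notice. It needs no new data, no added visit and no change to the sample size.
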